5 ADDITIONAL DATA ANALYSES

5.1 Interim Analyses

There is no planned formal interim analysis. A descriptive summary may be made during the study, if needed.

5.2 Other Analyses

5.2.1 Baseline Data Analyses

Subject demographics, medical history, EQ-5D-5L, Extended Prostate Cancer Index Composite (EPIC), Prostate Cancer Staging and Gleason score will be summarized using descriptive statistics. For continuous variables, the descriptive statistics will include mean, standard deviation, minimum and maximum. For discrete variables, frequency tables will be displayed. No formal statistical testing will be performed.

5.2.2 Procedure Analyses

Procedure information such as anesthesia, SpaceOAR dosage, intraoperative device usage, device defects, complications, etc. will be summarized using descriptive statistics for continuous and frequency with percentages for discrete variables. No formal statistical testing will be performed.

5.2.3 Post-procedure Analyses

Post-procedure information will be collected at 30 days and will be summarized using descriptive statistics for continuous and frequency tables or proportions for discrete variables. No formal statistical testing will be performed.

5.2.4 Patient disposition/status

Subject Disposition of follow-up Compliance will be provided at Post-procedure, 30days post procedure visit. A listing for deaths will be provided with relatedness to study device and study procedure, with date of death and duration of days from index procedure date.

5.2.5 Analysis of Adverse and Serious Adverse Events

Frequency of site reported Serious adverse events and Non-serious adverse events associated with the study device will be summarized. The events will be summarized by MedDRA system organ class and MedDRA system preferred terms with event counts and proportions. A listing based on all site reported adverse events with seriousness, relationships and duration days will be created. Similarly, a listing for all anticipated/unanticipated adverse device events with seriousness and duration from onset date will be also produced.

For calculating events and rates, ‘Events numbers’ are total number of episodes for each type of event among all subjects. ‘Rate of Subjects with Event’ numbers are percent of subjects who experienced one or more episodes of the event. ‘Events’ numbers for “TOTAL” are the sum of the individual event category totals. ‘Rate of Subjects with Event’ numbers for “TOTAL” is the percent of subjects who experienced at least one adverse event.

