The SpaceOAR System has been marketed in Australia, Canada, Japan, Europe and USA. A pilot study of SpaceOAR System in Europe enrolled 52 subjects. The objective of the Pilot Study was to evaluate the initial safety and effectiveness of SpaceOAR System when it is injected between the rectum and prostate in adult men undergoing external beam radiation therapy for treatment of low-to-mid risk prostate cancer. The space creation effect of SpaceOAR hydrogel was assessed via co-primary effectiveness endpoints. Analysis of the endpoints for the Per Protocol Population showed that³⁴, Functional Success, defined as the creation of at least 7.5 mm space between the prostate (Mid-gland) and rectum measured on CT or MRI, was achieved in 46 of 48 subjects (95.8%). Clinical Success, defined as reduction in radiation dose to the anterior rectum as measured by a 25% or greater reduction in rV70 (i.e., the percent volume of the rectum receiving at least 70 Gy) was achieved in 44 of 46 subjects (95.7%). There were no unanticipated adverse events associated with the SpaceOAR System procedure or the SpaceOAR hydrogel. These results from the Pilot Study established initial safety and performance for use of the SpaceOAR System as a means to physically separate the rectum from the prostate and reduce the rectal radiation dose.

The pivotal study of SpaceOAR System in USA aimed to evaluate the safety and effectiveness of the SpaceOAR System when it is used in patients with a pathologically confirmed diagnosis of clinical stage T1 or T2 prostate cancer who were indicated for a course of IMRT. 222 eligible subjects were enrolled and were randomized (2:1) to the Treatment group (SpaceOAR System) or Control group after successful fiducial marker placement. The study showed that hydrogel placement success rate was 99%; Perirectal spaces were 12.6 ± 3.9 mm and 1.6 ± 2.0 mm in the spacer and control groups, respectively. There were no device-related adverse events, rectal perforations, serious bleeding, or infections within either group. The reduction of rectal V70 in treatment group was significantly more than control group (12.4% to 3.3%, P<.0001). Overall acute rectal adverse event rates were similar between groups, with fewer spacer patients experiencing rectal pain.

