17.1. Anticipated Adverse Events and Anticipated Adverse Device Effects

Potential Anticipated adverse events and Anticipated Adverse Device Effects that may be associated with the use of SpaceOAR System include, but are not limited to:

- Pain associated with SpaceOAR hydrogel injection
- Pain or discomfort associated with SpaceOAR hydrogel
- Local inflammatory reactions

Confidential

- Infection
- Urinary retention
- Mucosal damage, ulcers
- Bleeding
- Constipation
- Urgency(eg urinary and rectal)
- Allergic reaction
- Embolism
- Fistula
- Penetration
- Syncope

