	Provide all relevant source documentation (de-identified/ pseudonymized) for reported event.	
 Upon request of sponsor

Event Classification	Communication Method	Communication Timeline (EU MDR 2017/745, MDCG 2020-10/IMEDDEV 2.12/1: GUIDELINES ON A MEDICAL DEVICE VIGILANCE SYSTEM)
Adverse Event including Adverse Device Effects	Complete AE eCRF page, which contains such information as date of AE, treatment of AE resolution, assessment of seriousness and relationship to the device.	
 • In a timely manner but recommend within 10 business days after becoming aware of the information for retrospective and prospective cohort • Upon request of sponsor
	Provide all relevant source documentation (de-identified/ pseudonymized) for reported event.	

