3 ENDPOINT ANALYSIS

3.1 Primary Safety/Effectiveness Endpoints

Primary Effectiveness Endpoint: The distance between the posterior prostatic capsule and anterior rectal wall post SpaceOAR hydrogel administration.

Measurement: The distance between the posterior prostatic capsule and anterior rectal wall is measured on the axial image slice closest to halfway between apex and base, from posterior edge of prostate to inner rectal wall.

Primary Safety Endpoint: AEs related to SpaceOAR system and/or procedure within 30 days following procedure will be observed.

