3.1.3 Statistical Methods

Descriptive statistics (mean, median, SD, min and max) along with corresponding 95% confidence interval will be used to summarize the effectiveness endpoints, such as distance between the posterior prostatic capsule and anterior rectal wall post SpaceOAR hydrogel administration. One sample t-test will be used to calculate the p-value for

primary effectiveness endpoint. To summarize safety endpoint, AEs related to SpaceOAR system and/or procedure within 30 days will be tabulated with frequencies, percentages along with the 95% confidence intervals.

This study may allow explorative statistics based on collected data, including but not limited to: risk factors associated with functional failure.

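### SAP 5.2.5 words the only MedDRA-coded adverse-event summary for device-associated events, while the primary safety endpoint covers device and/or procedure (minor)

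*SAP*

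**What the plan says.** The primary safety endpoint is the same in Protocol 6.2.1.2 and SAP 3.1: "AEs related to SpaceOAR system and/or procedure within 30 days following procedure will be observed". SAP 3.1.3 plans its table on that definition: "AEs related to SpaceOAR system and/or procedure within 30 days will be tabulated with frequencies, percentages along with the 95% confidence intervals".

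SAP 5.2.5, which sits under the additional analyses of Section 5, then describes the general AE output. Its opening sentence sets the scope: "Frequency of site reported Serious adverse events and Non-serious adverse events associated with the study device will be summarized". The next sentence sets the format: "The events will be summarized by MedDRA system organ class and MedDRA system preferred terms with event counts and proportions". The section also promises a full listing: "A listing based on all site reported adverse events with seriousness, relationships and duration days will be created". Its second paragraph defines a total row, whose subject rate is the percentage of subjects with at least one AE of any kind. That definition mentions neither relationship nor a 30-day limit.

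Elsewhere the documents treat device and procedure as two separate relationships:

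- Protocol 18.1 lists device-related and procedure-related AEs as separate reportable categories.
- Protocol 18.3 requires the investigator to judge each reportable AE against the device and/or the procedure.
- SAP 5.2.4 gives both relationships in the listing of deaths.
- SAP 7.4 describes AE rates as covering both.

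**The concern.** The coded summary is where a reader sees which events occurred, how often, and in how many subjects. For a device placed by transperineal injection, one would expect it to break down the same events that make up the primary safety endpoint. As worded, it covers a different set. Because the documents keep the two relationships apart, a programmer has good reason to read the 5.2.5 wording literally and filter on the device relationship alone.

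Two things follow. Events attributed only to the procedure would have no breakdown by system organ class and preferred term. The report would also show a 30-day related-AE percentage in one table and a total in another, with no stated way to get from one to the other.

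**Working it through.** The plan gives no figure to reproduce on this point, so the check is to classify events and see which output takes each one.

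The first sentence of SAP 5.2.5 can be read in two ways. In reading A, the device restriction applies to serious and non-serious events. In reading B, it applies to non-serious events only and all serious events are summarised.

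| Event within 30 days | 3.1.3 tabulation | 5.2.5 coded, reading A | 5.2.5 coded, reading B | 5.2.5 listing of all AEs |
|---|---|---|---|---|
| Device-related, serious or not | yes | yes | yes | yes |
| Procedure-only, non-serious | yes | **no** | **no** | yes |
| Procedure-only, serious | yes | **no** | yes | yes |
| Unrelated, serious | no | no | yes | yes |
| Unrelated, non-serious | no | no | no | yes |

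1. **Non-serious procedure-only events** are outside the coded table under both readings. This does not depend on how the sentence is parsed.
2. **Serious events** depend on the reading. Under A, procedure-only serious events are left out. Under B, unrelated serious events are added.
3. **The total row** matches the 3.1.3 percentage by construction under neither reading. Reading A is too narrow. Reading B is too narrow for non-serious events and too wide for serious ones. If the total is taken literally as any AE, it is too wide, because it also takes in the last row.
4. **Time window.** SAP 5.2.5 states no 30-day limit. The follow-up visit in the data collection schedule is at 30 days ± 7, so it can fall as late as day 30 + 7 = 37. An event on days 31 to 37 could enter the coded table but lies outside the endpoint.

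Size of the mismatch under reading A, with the total restricted to the tabulated events: let N be the number of treated subjects and k the number whose only related events are procedure-only. Both rates have denominator N, so within 30 days

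difference = k / N.

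At the planned maximum of N = 20, each such subject contributes 1/20 = 5 percentage points. The documents give no basis for a value of k, so only the size per subject can be stated.

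**The case against.** The strongest reply is that the endpoint itself is fully covered. SAP 3.1.3 tabulates device and/or procedure events with percentages and confidence intervals, and SAP 5.2.5 is a supplementary analysis. With at most 20 subjects, the listing of all AEs shows every event with its relationships. All of that stands, and it limits the point to the coded breakdown and its total. What remains is that 3.1.3 does not specify MedDRA coding or event counts, and a listing gives no rates.

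Three stronger readings are tempting, and the documents do not support them.

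- *Injection-related events disappear from the main safety table.* They do not. The table for the primary safety endpoint is the one in SAP 3.1.3, and it includes them.
- *Relationship to the procedure is not collected.* A reader might infer this from Table 18-3 of Protocol 18.4, where the contents of the AE page end with "assessment of seriousness and relationship to the device". That list is introduced as examples of what the page holds. Protocol 15.2 and 18.3 require the procedure relationship to be assessed, Protocol 18.1 makes procedure-related AEs reportable, and Protocol 16 describes the relationship to device and procedure as recorded in the CRF. No data gap is shown, and no protocol change is needed.
- *The coded table could be empty while injection harms occur.* Protocol 4.1 says of the pivotal study: "There were no device-related adverse events, rectal perforations, serious bleeding, or infections within either group". That does not predict attribution here. The adverse device effect definition in Table 18-1 takes in events arising from inadequacies in deployment and implantation, and from use error. Protocol 17.1 puts "Pain associated with SpaceOAR hydrogel injection" among the events that may be associated with use of the system. Table 18-2 classes a weak or unassessable relationship as possible. Some injection events may therefore be called device-related. How many is a matter for the sites.

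**Conclusion.** The point holds as a minor inconsistency in the SAP. The coded AE summary in SAP 5.2.5 is scoped to the device, whereas the endpoint it should break down is scoped to device and/or procedure. On either reading, non-serious procedure-only events have no coded breakdown. For serious events the text is ambiguous. The total row has no defined link to the primary safety percentage.

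The size is 5 percentage points per affected subject at N = 20. This assumes that the total keeps the device restriction and that the subject has no device-related event. If no event is judged procedure-only, this gap is zero.

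The primary safety result, the effectiveness decision rule and data collection are unaffected.

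**What to change.** Amend SAP 5.2.5 before the tables are programmed:

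1. Replace the device-only restriction with *related to the study device and/or the study procedure*.
2. Present the events within 30 days by system organ class and preferred term in three columns: device, procedure, and either. Define the total of the *either* column so that its subject rate equals the SAP 3.1.3 percentage.
3. State that serious AEs are summarised regardless of relationship, in their own block, so that unrelated serious events do not disturb that match.

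SAP 5.3 already provides for an amended SAP approved before the analysis. The cost is slightly more table programming from data that Protocol 18.3 already requires. No new subjects, visits, data items or protocol amendment are needed.

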5.2.6 Protocol Deviations

Deviations from Investigational Protocol collated during procedure and post procedure for all the planned events as specified in protocol will be captured and summarized. A table summarized with counts and percent and another summary table presented based on deviations reasons will be presented. A listing will be provided with deviation type, reason, visit and assessment/procedure requirement during the study for all subjects.

5.2.7 Device Deficiencies

A table will be produced for device deficiencies with count and percent by deficient components. A supported listing will be provided by subject, and if its leading to any event.

5.3 Changes to Planned Analyses

Any changes to the planned statistical analyses made prior to performing the primary endpoint analysis will be documented in an amended Statistical Analysis Plan which will be approved prior to performing the analysis. Changes from the planned statistical methods after performing the analysis will be documented in the clinical study report along with a reason for the deviation.

6 VALIDATION

All clinical data reports generated per this plan will be validated per 90702587, Global WI: Clinical Data Reporting Validation. The validation level R1 chosen for all primary,

secondary, safety and other additional endpoints. The validation program includes checking logs and generating compare reports in comparing with main programming datasets. Statistical analyses and validation will be performed by IQVIA team.

7 PROGRAMMING CONSIDERATIONS

All statistical programming tasks will be performed by IQVIA™ independently.

7.1. Statistical Software

All statistical analyses will be done using The SAS System Version 9.2 software or above (Copyright © 2000 SAS Institute Inc., [name]. All rights reserved.).

7.2. Format of Output

Statistical analysis will be performed using SAS. All output for the final statistical report will be in the form of a Word document, which may include tables, figures, graphs, and listings, as appropriate.

7.3. Rules and Definitions

For baseline categorical variables, subjects with missing values will not be counted in the corresponding denominators for proportions. Number of patients completing the visit will be considered in denominators.

7.4. Handling of Missing/Partial Date

Missed or late visits will be recorded as Protocol Deviations.

When calculating rates of all adverse events, both device and/or procedure related with missing event date (i.e. mm/dd/yyyy), every effort should be made to work with safety and/or data management representatives to query sites for missing data. However, in the situations when it cannot be resolved, missing and partial missing dates may be handled as using the worst-case scenario as follows:

Partial Date Description	Action taken
Entire onset date is missing	The procedure date will be used for the onset date.
The month and the day of the month are missing but the year is available	January 1 st will be used for the month and day of the onset date. However, if the imputed date falls before the procedure date, then the procedure date will be used for the onset date.
Day is missing, but the month and year are available	The 1 st will be used as the day of the onset date. However, if the imputed date falls before the procedure date, then the procedure date will be used for the onset date.
